11.3.1 Immediate reporting

11.3.1.1 Reporting of SAEs to sponsor

SAEs observed throughout the study must be documented on an "SAE report" form in accordance with instructions for completing the "SAE report" form. This form and the instructions will be provided in the investigator file and must be completed and supplied immediately (within 24 h) to the sponsor (21CFR§ 312.32, 21CFR§ 312.64).

Any SAE that occurs throughout the study, whether or not related to the IMP or the medical device, must be reported by the investigator within 24 h by fax, or by e-mail, to the following contact data:

Email: [REDACTED]

Fax: [REDACTED]

The initial report must be as complete as possible, including details of the current disease and (serious) AE, and an assessment of the causal relationship between the event and the IMP or IMD or study procedures.

Information not available at the time of the initial report (e.g. an end date for the AE or laboratory values received after the report) must be documented on an “SAE report” form, with the box “Follow-up”/“Final report”.

The instructions for completing the “SAE report” form give more detailed guidance on the reporting of SAEs, and AEs initially reported as non-serious that become serious. In the latter situation, when a non-serious event becomes serious, details must be forwarded immediately (within 24 h) to the sponsor on an “SAE report” form.

Note:

For regulatory reporting purposes, events which are assessed by the sponsor as “unrelated” or “unlikely related” to the study medication will be considered as having no reasonable causal relation and will not be reported on an expedited basis.

Events assessed by the sponsor as “possibly, probably or definitely related” will be considered as having a plausible causal relation to the study medication and will be reported if they are also considered unexpected and serious.

The sponsor will ensure that all legal reporting requirements to the competent authorities and the IRB(s) are met (see [Section 11.4.2](#)).

11.3.1.2 Reporting of pregnancies to sponsor

Pregnancies occurring during a subject's participation in the study, although not typically considered SAEs, must be notified to the sponsor within the same timelines as an SAE (within 24 h after becoming aware of the pregnancy) on a pregnancy notification form. Further treatment will be addressed on a case-by-case basis with the treating physician and the investigator.

Any pregnancy should be followed up until completion. If relevant, the development of the newborn will be monitored for an appropriate time post-delivery.

The pharmacovigilance department of the sponsor or designee has to be notified by fax or e-mail.

11.3.1.3 Reporting of USADEs to the sponsor and to IRB

Events which can be clearly assigned to the IMD and which are assessed by the investigator as “possibly, probably or definitely related” to the IMD and which are both serious and unanticipated will be considered as unanticipated serious adverse device effect (USADE). A report of any USADE occurring during an investigation shall be submitted to the reviewing

IRB and the sponsor within 10 working days after the investigator first learns of the effect (21 CFR §812.150).

In case a serious and unexpected event cannot be clearly assigned to the IMD, it should be treated as an SAE (see [Section 11.1.2](#)).

Note: Reporting of USADEs to the sponsor is equal to SAE reporting described in [Section 11.3.1.1](#).

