 - if the AE is related to IMP only, IMD only, or both (cannot be ambiguously assigned to one of both).
- **For new lesions:** inside or in close proximity (< 10 cm distance) to the treatment field
- The causality/relatedness of AEs has to be assessed:
 - UNRELATED: AEs that are judged to be clearly and incontrovertibly due to a cause other than the IMP/IMD and study procedure (concomitant disease etc.).
 - UNLIKELY RELATED: the temporal sequence is atypical, and the AE does not follow a known pattern of response to IMP/IMD another causative factor is present but causal role of the study drug cannot be excluded.

- **POSSIBLY RELATED**: either an event that is temporally associated with the use of the IMP/IMD or a known pharmacological effect/associated reaction, which is also recognized with another concomitant therapy/disease or other external cause.
- **PROBABLY RELATED**: appropriate temporal association, known pharmacological effect, recognized to be an associated IMP/IMD reaction and for which no other possible cause is evident.
- **DEFINITELY RELATED**: the reaction has occurred with this IMP/IMD previously (i.e. positive re-challenge) and there is an appropriate temporal relationship between therapy and reaction; and the reaction follows a known or expected response pattern to the suspected drug.

The investigator should use medical judgment to determine whether he/she assumes a reasonable causal relationship, including into his/her evaluation all relevant factors and factual evidence such as

- temporal course and latency
- results from re-challenge
- pattern of the reaction
- known pharmacological properties of the product
- and alternative explanations (e.g. other drugs, medical history, concomitant diseases).

Every attempt should be made to describe the AE in terms of a diagnosis. If a clear diagnosis has been made, individual signs and symptoms will not be recorded as separate AEs unless they represent atypical or extreme manifestations of the diagnosis, in which case they should be documented as separate events. In the case of SAEs or SARs, respectively, component signs and symptoms may be recorded in addition to a diagnosis if they further clarify the clinical picture. If a clear diagnosis cannot be established, each sign and symptom must be recorded individually.

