## 4.4 Analysis of Endpoints

### 4.4.1 Adverse Events

AEs will be coded by using the Medical dictionary for regulatory activities (MedDRA, MedDRA version available at the day of database closure). If an AE occurs in multiple treatment areas, it is reported separately for each treatment area within the eCRF. Thus, some AEs are counted repeatedly for the analysis.

Analysis will focus on severity and duration of TEAEs. TEAEs are defined as all AEs with onset or worsening after treatment with IMP up to Visit 5 (Final visit). AEs with start on the day of PDT which are unrelated or unlikely related to IMP belonging to AE category 'NEW LESION' and with action taken 'PDT treatment' will be classified as pre-treatment emergent adverse events. If unclear due to incomplete start date/time of AE or IMP application or uncertainty about worsening of AE, AEs will be assumed as TEAEs. AEs developing between signing the ICF and IMP application at Visit 2 will be considered as pre-treatment adverse events (PTAEs). TEAEs as defined above, will be tabulated by system organ class (SOC) and preferred term (PT) (MedDRA). The number of entries, as well as the number and rate of affected subjects will be reported for each treatment area and overall.

TEAEs will also be tabulated by relationship to IMP and/or medical device and by worst severity. TEAEs are considered being related to IMP or medical device, if causal relationship between IMP or medical device and the TEAE is at least possible or relationship assessment is missing. For AEs with changes in severity, the worst severity per AE and subject will be tabulated.

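### Read literally, the protocol keeps a serious unexpected event that is possibly lamp-related, but neither clearly assigned to the lamp nor likely drug-related, out of the sponsor's expedited reports

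*Protocol*

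**What the plan says.** **Definition of a USADE (protocol 11.3.1.3).** The definition covers "Events which can be clearly assigned to the IMD and which are assessed by the investigator as" at least possibly related to the lamp, provided they are also serious and unanticipated. The remainder is redirected: "In case a serious and unexpected event cannot be clearly assigned to the IMD, it should be treated as an SAE".

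**Expedited reporting of SAEs (Note in protocol 11.3.1.1).** The test is the sponsor's view of causality. Events that the sponsor places in the two lowest causality categories with respect "to the study medication will be considered as having no reasonable causal relation and will not be reported on an expedited basis". Those rated possibly related or higher "will be considered as having a plausible causal relation to the study medication and will be reported if they are also considered unexpected and serious". Neither sentence mentions the lamp.

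**Sponsor's general rule (protocol 11.4.2).** Serious unexpected events for which the sponsor reasonably suspects a causal link go to FDA and all investigators as IND safety reports. No product is named. A separate sentence sends USADEs to FDA, the IRBs and all investigators.

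**Attribution on the AE page (protocol 11.3).** The investigator records "if the AE is related to IMP only, IMD only, or both", the last being for events that cannot be assigned to one product. The strength of the relation is a separate item.

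**Deadlines.** Under 11.3.1.3 a USADE report goes to the reviewing "IRB and the sponsor within 10 working days after the investigator first learns of the effect". The closing note of the same section adds: "Reporting of USADEs to the sponsor is equal to SAE reporting described in" 11.3.1.1, where the limit is 24 h.

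**The concern.** In this treatment drug and light act together, so a clear assignment to one of them will often be impossible. The USADE sentence nevertheless asks for clear assignment and, in the same breath, accepts a merely possible relation. An event that fails the first condition moves to a route whose stated filter looks only at the drug.

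The lamp is the component for which this matters most. Protocol 4.1 calls it a new medical device, 8.1.2 says it is not yet approved in the US, and illumination with it is part of the study objective. Protocol 11.1.5 expects no adverse effects from the lamp itself when it is used properly, so a serious one would probably count as unanticipated. At stake is whether FDA and the other sites, which use the same type of lamp, are told promptly of a possible device effect that falls short of certainty.

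**Working it through.** No sample size, power or event count bears on this point, and the plan gives no figure to reproduce. The check is to follow a serious, unexpected event through protocol 11.3, 11.3.1.1, 11.3.1.3, 11.3.1.4 and 11.4.2 for each possible attribution.

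1. **Drug only, at least possible.** Not a USADE. The second sentence of the Note requires an expedited report. No gap.
2. **Clearly the lamp, at least possible.** A USADE. The Note read alone would exclude it as unrelated to the medication, but the USADE sentence in 11.4.2 sends it to FDA, the IRBs and all investigators. No gap in practice, though the two texts disagree.
3. **Drug and lamp cannot be separated.** The event is not clearly the lamp's, so it takes the SAE route and loses the device reporting line. It will normally be at least possibly drug-related, so the Note still requires an expedited report.
4. **Possibly the lamp, not clearly assigned to it (for example because a concomitant disease is another explanation), and unlikely to be the drug.** Not a USADE, so the USADE sentence in 11.4.2 does not apply. On the SAE route, the first sentence of the Note excludes it from expedited reporting.

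Case 4 is the gap. USADE status rests on the investigator's assessment, and the Note on the sponsor's. An event that the investigator marks as due to both products, but the sponsor rates unlikely drug-related, therefore also ends in case 4.

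**What still happens in case 4.** The investigator must send any SAE to the sponsor within 24 h whatever its relation to drug or device (11.3 and 11.3.1.1). The investigator must also report to the IRB all unanticipated problems that put people at risk (11.3.1.4).

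**Does 11.4.2 close the gap?** Its general rule names no product and could be read to include the lamp. But it turns on reasonable suspicion of causality, and the Note, in the section that refers the reader to 11.4.2, has just defined the absence of a reasonable causal relation by the medication alone. The two sections conflict, and neither is said to prevail.

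**Deadlines.** At 5 working days per week, 10 working days are 10 / 5 × 7 = 14 calendar days. The closing note of 11.3.1.3 gives 24 h, or 1 day. These are two limits for the same report to the same recipient. A report made within 24 h satisfies both.

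**The case against.** **The two conditions can be read as compatible.** Protocol 11.3 collects which product is suspected and how strongly as separate items. Clear assignment may mean the lamp rather than both products, with the degree of relation judged separately. On that reading a lamp-only, possibly related event is a USADE. This is fair and shrinks case 4, but the section does not say it. It also leaves the event marked as both that the sponsor rates unlikely drug-related.

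**Other safeguards exist.** These include the product-neutral rule in 11.4.2, the promise in 11.3.1.1 to meet all legal reporting requirements, the reporting of device effects in 11.1.5, the IRB duty in 11.3.1.4, and the continuous benefit-risk monitoring in 11.5, which covers the lamp. They stand, and they rule out an event simply disappearing. None tells staff that the drug-only exclusion in the Note does not apply.

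**Stronger readings that the documents do not support.**
- A reader might infer that such an event can go wholly unreported. It cannot: it reaches the sponsor as an SAE and stays under the investigator's duty to the IRB.
- A reader might infer that the sponsor hears of a device event two weeks late, and turn that delay into a count of further subjects treated. That requires a site to ignore 11.3, 11.3.1.1 and the closing note of 11.3.1.3. It also assumes that notifying the sponsor would stop dosing, which these sections do not say.
- A reader might see a conflict with SAP 4.4.1, which counts a TEAE as related "if causal relationship between IMP or medical device and the TEAE is at least possible or relationship assessment is missing". That is a rule for tables and does not govern expedited reporting. It does mean that the report could tabulate a serious device-related event that was never handled as a device event.

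**Conclusion.** The point holds in a limited form. A stated rule, the Note in 11.3.1.1, excludes from expedited reporting a serious unexpected event that is possibly lamp-related, not clearly assigned to the lamp and unlikely to be drug-related. The more general wording of 11.4.2 contradicts that rule without clearly overriding it. What can be missed is the sponsor's expedited report to FDA and the other investigators.

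The conclusion assumes a literal reading of the Note and of the clear-assignment condition. The documents give no rate for such events, so their expected number cannot be stated; the class is narrow. The two sponsor deadlines are a drafting conflict only. No endpoint, analysis or sample size is affected. The text should still be changed, because it governs safety reporting on an unapproved device and is cheap to correct.

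**What to change.** - **11.3.1.3, definition:** remove the clear-assignment condition. Define a USADE as any serious, unanticipated event at least possibly related to the IMD, whether or not the IMP is also suspected. Adapt the sentence that redirects unassigned events to match.
- **11.3.1.1, Note:** exclude only events rated unrelated or unlikely related to both the study medication and the IMD. Include events at least possibly related to the study medication, the IMD or both. The word both matters in the exclusion: with or, an event due to the lamp alone could still be excluded for being unrelated to the drug.
- **11.4.2:** state that the suspected causal relation may be to the IMP, the IMD or both.
- **11.3.1.3, deadlines:** reconcile the deadline sentence with its closing note, so that the sponsor and the IRB each have one stated limit.

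The cost is wording in three protocol sections and in the site safety-reporting instructions, made by amendment. The downside is that a few events may be reported under both the drug and the device routes. The SAP needs no change.

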11.3.1.4 Expedited reporting of adverse events to IRB

The investigator will promptly forward IND safety reports received from sponsor (see [Section 11.4.2](#)) and report all unanticipated problems involving risk to human subjects or others, and changes in the research activity to the IRB. The sponsor may submit IND safety reports directly to the IRB on the investigator's behalf. Please refer to section [11.4.2](#).

11.3.2 Unblinding

This is an open-label study, i.e., unblinding is not applicable.

11.4 Documentation and reporting of adverse events by sponsor

11.4.1 Determination of expectedness, Reference Safety Information

Expectedness of serious AEs will be determined by the sponsor according to the designated Reference Safety Information (RSI). Any updates or substantial amendments will be considered accordingly. The RSI for the investigational products will be included in the current IB.

Unexpected: An AE or suspected adverse reaction is considered unexpected if it is not listed in the RSI or is not listed with the specificity or severity that has been observed. Unexpected, as used in this definition, also refers to AEs or suspected adverse reactions that are mentioned in the RSI as occurring with a class of drugs or as anticipated from the pharmacological properties of the drug, but are not specifically mentioned as occurring with the particular drug under investigation.

11.4.2 Expedited reporting of adverse events to competent authorities and investigators

The sponsor will report all serious and unexpected AEs, which are judged by the sponsor as having a reasonable suspected causal relationship (unexpected serious suspected adverse reaction) as IND safety reports to the FDA and all participating investigators according to applicable law.

The sponsor will also report USADEs to the FDA, all reviewing IRBs and to all investigators.

The sponsor will submit IND safety reports directly to the IRB on the investigator's behalf, e.g. when the investigator submits to a central IRB, to avoid multiple submissions to the IRB. In these cases, the investigator receives confirmation that the report has been sent to the IRB by the sponsor.

11.4.3 Periodic reporting of adverse events by sponsor

A summary of all Investigational New Drug (IND) safety reports will be included in the progress report submitted annually to the competent authorities within 60 days of the international anniversary date of the product (14 June, in agreement with authorities). The same report will also be submitted to the IRB(s) to ensure a continuing review of the project.

11.4.3.1 Development safety update report (DSUR)

The sponsor will prepare and submit annual safety reports to competent authorities and concerned ethics committees.

11.5 Continuous risk assessment

The sponsor's pharmacovigilance department will apply appropriate monitoring measures to continuously survey the benefit risk ratio of the IMP, the IMD and study procedures.

12 WITHDRAWALS

12.1 Withdrawal of subjects

Subjects must be withdrawn from study (i.e. from any further study procedure) for the following reasons:

- At their own request (withdrawal of informed consent)
- If, in the investigator's opinion, continuation in the study would be detrimental to the subject's well-being
- Upon sponsor request

In all cases, the reason for and date of withdrawal must be documented. Subjects can withdraw consent at any time of the study without being obliged to specify a reason for their withdrawal. In case of an AE causing the withdrawal of consent, the AE has to be documented as cause of withdrawal.

In case of withdrawal after IMP administration the subject should be encouraged to come to a final visit for the conduct of safety assessments (physical examination, vital signs, safety laboratory including serum pregnancy test, if applicable, AEs and concomitant medication) as soon as possible.

In case of withdrawal before IMP administration, a final visit is not necessary. The subject will be considered as a drop-out. For subjects who are withdrawn before IMP administration only the date of informed consent, demographics and date and reason for withdrawal and (S)AEs, if applicable, have to be reported in the eCRF. The data will be listed separately from data of treated subjects.

A subject will be considered lost-to follow-up if he or she fails to return for scheduled visits and is unable to be contacted by the site. The investigator must make every effort to contact subjects lost to follow-up. Attempts to contact these subjects must be documented in the subject's records (e.g. times and dates of attempted telephone contact, e-mails or copies of letters send to the subject). At least three attempts should be performed and documented.

Discontinuation date is the date on which the investigator decides that no further attempt will be made to contact the subject and the subject is declared as lost-to follow-up.

12.2 Replacement of subjects

Subjects who discontinue will not be replaced.

12.3 Withdrawal of samples

Not applicable.

13.2 Emergency identification of investigational medicinal products

In this open-label study, all eligible subjects will receive one active treatment. For this reason, special emergency identification procedures are not applicable for this trial.

13.3 Emergency treatment

There is no substance-specific treatment for adverse reactions. For treatment of PDT associated pain and discomfort please see [Section 9.2](#).

During and after a subject's participation in the trial, the investigator or institution should ensure that adequate medical care is provided to a subject for any AEs, including clinically significant laboratory values, related to the trial. The investigator or institution should inform a subject when medical care is needed for intercurrent disease(es) of which the investigator becomes aware.

14 STATISTICAL PROCEDURES

14.1 General considerations

The principal features of the statistical analysis are described in this section. Technical details of the statistical analyses will be specified in a statistical analysis plan (SAP). The SAP will be finalized prior to the First-subject-first-visit for the final analysis of the study. The recommendations of the ICH E9 'Note for Guidance on Statistical Principles for Clinical Trials' including the addendum R1 to ICH E9 will be taken into account.

Unless otherwise stated, continuous data will be summarized by means of descriptive statistics, i.e. number of subjects, mean, standard deviation (SD), median, quartiles and range (minimum and maximum). Categorical variables will be summarized by absolute and relative frequencies (percentages) of subjects by category. Missing values will not be included in the calculation of percentages.

Eligible subjects who withdraw from study participation before IMP administration will be considered as dropouts.

The demographic data from screening failures and dropouts prior to IMP administration are entered into the clinical database and will not be passed through the data cleaning process. Their data are listed separately from data of treated subjects.

Statistical analyses will be conducted using SAS version 9.4 or higher (SAS Institute, 2010).

14.2 Analysis variables

Study objective

The objective of the study is to evaluate the safety and tolerability of BF-200 ALA PDT, utilizing BF-RhodoLED® XL illumination, in the treatment of mild to severe AK on the face and scalp in an expanded field-directed treatment.

The endpoints of the study are:

- Frequency and severity of adverse events (AEs), serious AEs (SAEs), and treatment-emergent adverse events (TEAEs). TEAEs are defined as all AEs with onset or worsening after treatment with IMP up to Visit 5
- Duration of TEAEs including the breakdown of severity category (mild, moderate, severe)
- Assessment of new lesions (AK, NMSC such as BCC, SCC or Bowens disease, and melanoma) if they occur inside the treatment field
- Assessment of new lesions (AK, NMSC such as BCC, SCC or Bowens disease, and melanoma) if they occur around the treatment field at a distance of < 10 cm
- Application site skin reactions during and post PDT, assessed by the investigator
- Application site discomfort during and post PDT, reported by the subjects
- Application site pain during illumination, as assessed by the subjects using an 11-point numeric rating scale

- Changes in vital signs
- Safety laboratory data
- Physical examination data
- Neurological assessments

